## **9.2. Follow up data collection**

### **9.2.1. COPD medications and treatments and concomitant medications**

COPD medications and treatments will be derived from medical records in site hospitals' Hospital Information System (HIS) complemented by site interview at each clinic visit including exacerbation visits and trimonthly telephone interviews including those not captured in HIS (e.g. purchased in pharmacies, prescribed by HCPs outside the research site hospitals). Pictures of COPD medication will be provided to assist patient recall during telephone interviews and clinic interviews.

Concomitant medications collected in this study will include: respiratory medications, antibiotics, oral steroids, gastroesophageal reflux disease (GERD) therapy, cardiovascular disease therapy and whether taking traditional Chinese medicines.

### **9.2.2. Smoking status**

Smoking status will be reassessed at each scheduled clinic visit evaluated by participants' self-report (e.g. never smoker, current smoker, former smoker).

### **9.2.3. Spirometry**

Spirometry (same measurements as baseline spirometry, refer to Section 9.1) will be performed in triplicate at time points listed in the SoA [Table 1](#). Spirometry assessments should be performed in accordance with ATS/ERS guidelines as outlined in the SRM. Predicted values will be based upon the spirometric reference values for Chinese [[Jian, 2017](#)].

### **9.2.4. COPD exacerbations**

COPD subjects will be asked for a history of AECOPD using components of moderate/severe exacerbation definition at each clinic visit including exacerbation visits. Additionally, COPD subjects will be contacted by phone every 3 months by the study staff and asked about their exacerbation details for the previous 3 months. Study staff will check Hospital Information System (HIS) during the interview to confirm the event of exacerbation wherever possible.

### **9.2.5. Clinically important deterioration (CID) components**

Clinically important deterioration (CID) is a new composite outcome (developed by GSK) for the prediction of future risk of long-term adverse outcomes. In this study, the CID will be derived from three key clinical assessments, which are 1) count of moderate/severe exacerbations, 2) worsening of FEV1, and 3) change in the CAT score measured over 6 months. CID was defined as: decrease of  $\geq 100$  mL in post-bronchodilator FEV1, or increase of  $\geq 2$  units in the CAT, or an occurrence of a moderate/severe exacerbation.

### **9.2.6. Patient Reported Outcome Measures**

All Patient reported outcome measures should be collected in a nice, quiet setting without distractions (e.g., television, cell phones).

The COPD Assessment Test (CAT) will be collected at the beginning of study visits where applicable, before any other procedure.

The modified Medical Research Council (mMRC) Dyspnea Scale and St. George's Respiratory Questionnaire for COPD (SGRQ-C) will be administered at baseline.

The EXAcerbation of COPD Tool (EXACT) will be administered each evening among sub-cohort participants using an electronic diary.

COPD Assessment in Primary Care to Identify Undiagnosed Respiratory Disease and Exacerbation Risk (CAPTURE) will be administered at baseline and Visit3.

#### **9.2.6.1. COPD Assessment Test (CAT)**

The COPD Assessment Test (CAT) is a validated, short and simple patient completed questionnaire which has been developed for use in routine clinical practice to measure the health status of patients with COPD [[Jones, 2009](#); [Jones, 2012](#)]. The CAT is an 8-item questionnaire suitable for completion by all patients diagnosed with COPD. When

completing the questionnaire, participants rate their experience on a 6-point scale, ranging from 0 (no impairment) to 5 (maximum impairment) with a scoring range of 0-40. Higher scores indicate greater disease impact [[Jones](#), 2009, CAT website].

For all participants, CAT will be completed at baseline, each follow up clinic visit, and tri-monthly phone interviews. Interviewer-administered approach (face-to-face or over the phone) will be used.

Additionally, for monitoring purpose, monthly CAT will be interviewer-administered over phone call in the sub-cohort for 6 months after baseline visit and 6 months after Visit 3. CAT will also be assessed in the sub-cohort at exacerbation visits.

#### **9.2.6.2. Evening Diary (sub-cohort only)**

Participants in the sub-cohort will complete an eDiary each evening consisting of the 14 item EXACT and additional questions as described below. Participants will be trained to use the eDiary at baseline visit and will complete the diary each evening in line with SOA.

- Exacerbations of Chronic Pulmonary Disease Tool (EXACT) and Evaluating Respiratory Symptoms in COPD (E-RS: COPD)***

The Exacerbation of Chronic Pulmonary Disease Tool-Patient Reported Outcomes (EXACT) is a 14-item participant reported outcome instrument designed to capture information on the occurrence, frequency, severity, and duration of symptoms suggestive of an exacerbation of disease in participants with COPD. EXACT captures information on the severity of the respiratory and systemic manifestations of a COPD exacerbation as reported by the participant [[Leidy](#), 2013].

The Evaluating Respiratory Symptoms in COPD (E-RS: COPD) consists of 11 items from the 14-item EXACT instrument. The E-RS: COPD is intended to capture information related to the respiratory symptoms of COPD, i.e. breathlessness, cough, sputum production, chest congestion, and chest tightness. The E-RS: COPD has a scoring range of 0-40, with higher scores indicating more severe symptoms [[Leidy](#), 2014]. Three subscales of the E-RS: COPD are used to describe different symptoms: breathlessness, cough and sputum, and chest symptoms.

The EXACT questionnaire will be completed each day at bedtime in the daily digital diary during the pre-defined study period. EXACT events will be identified from the 14 EXACT questions. Changes in overall symptoms and in the subscales of breathlessness, cough and sputum, and chest symptoms will be measured using the E-RS: COPD subset of EXACT.

- Additional questions***

In addition to the collection of EXACT, participants will also complete 5 additional daily diary questions to provide the information on other symptoms suggestive of an exacerbation: sputum purulence (color), wheezing, sore throat, colds (nasal discharge and/or nasal congestion) and fever without other cause.

The additional symptoms questions, combined with EXACT responses to questions on dyspnea, cough and sputum quantity will be assessed in stream and used to trigger prompts to both site and patients about symptom changes that may be indicative of an exacerbation.

#### **9.2.6.3. Other PRO assessments**

[figure not shown]
Chronic mucus hypersecretion (CMH) is defined as: At least 3 months of cough & phlegm in past year. This will be identified by asking a question as “How many months in the past 12 months have you had bronchitis or chronic coughing with phlegm or sputum from the chest?” Meanwhile, SGRQ-C and the CAT will be used for identification of CMH in this study. This would be identified by cough and phlegm related questions in SGRQ-C or CAT (details to be specified in the RAP).

The SGRQ-C is a disease-specific questionnaire designed to measure the impact of respiratory disease and its treatment on a COPD patient’s HRQL [Meguro, 2007]. The SGRQ-C is a recent adaptation of the SGRQ instrument and the resulting SGRQ-C scores is transformed into the one equivalent to the original instrument.

The CATPURE is a short, five-item questionnaire that can be easily completed by patients and are used to identify individuals who may have undiagnosed, clinically significant COPD.

#### **9.2.7. Computed tomography (CT) (sub-cohort only)**

CCI

Inspiratory and expiratory HRCT scans are required at Visit 1(baseline) and Visit 4 (the end of study), while only inspiratory scan will be conducted on exacerbation visit.

HRCT on the study participants may reveal the presence of previously undiagnosed malignant or other suspicious lesions (nodules). A local radiologist will review the HRCT scans solely for this purpose and notify the PI of any such observations. The radiologist should notify the PI of any observations within a week of the HRCT. The PI will then notify the subject’s own doctor, who will be responsible for referral to further medical care. The follow up care will be in line with local hospital or clinic procedures for dealing with nodules.

#### **9.2.8. Digital physical activity (sub-cohort only)**

Daily digital steps will be collected in sub-cohort only. Participants are required to keep wearing the wrist band for 1 month from visit 1 and 3 as outlined in the time and event table.

### **9.2.9. Biomarker(s)**

#### **9.2.9.1. Blood biomarkers**

Blood samples will be taken at Visit 1 and throughout the study as defined in the Time and Events Table. ([Table 1](#))

- Plasma fibrinogen, hsCRP, total/differential blood cell count measurements and haemoglobin will be conducted at central lab for all participants
- Additional protein analysis will be conducted at central lab for the sub-cohort using validated assays. Analytes chosen will include serum sRAGE, CC16 and IP-10, HbA1c.

The blood biomarker assessments will be conducted according to the study reference manual.

#### **9.2.9.2. Sputum microbiome and sputum cytology (sub-cohort only)**

Sputum samples for microbiome and sputum cytology will be collected in sub-cohort only as defined in the Time and Events Table ([Table 1](#)). Sputum can be collected spontaneously or can be induced, as per investigator judgement, induced sputum is preferred. Sputum sampling should only be done if, in the opinion of the investigator, it is safe for the subject. The sputum microbiome and sputum cytology assessments will be conducted according to the sputum assessment procedure (Refer to study reference manual).

Additional analyses may include the measurement of viruses and fungi.

### **9.2.10. Healthcare Resource Utilization and Cost**

To reflect the routine medical care, the information on COPD-related healthcare resource utilization and cost occurred within site hospitals will be captured on the study questionnaire form where possible using the HIS (based on site feasibility). Information collected include:

- Unscheduled COPD outpatient visits and emergency visits
  - Number of visits, date of visit, diagnosis of visit, cost
- COPD hospitalization (including intensive care)
  - Number of hospitalization, date and length of stay, diagnosis of visit, cost
- Prescribed COPD medications
  - Medication name, date of prescription, dosage, administration, cost, whether the prescription is picked up at hospital, etc.
- Other COPD treatment, e.g. oxygen therapy, nebulizers
  - Treatment name, date, cost, etc
- Lab tests, image tests, surgeries, and other tests and procedures (e.g., spirometry, Chest X-Ray, CT)
  - Test or procedure, date of operation, cost, etc.

- Healthcare cost if feasible, e.g. general service usage, consultation fee
  - Item, date of charge
- Insurance coverage and patient out-of-pocket payment if feasible

In addition, healthcare resource utilization could occur in other places outside of the site hospitals including: (1) hospitals other than the site hospital where the subject is recruited; (2) retail pharmacy stores; (3) subjects' home. Healthcare resource utilized and associated costs will be collected using standard questionnaires at trimonthly subjects' phone interviews. Information collected include COPD-related diagnosis and treatment in the above sources:

- Outpatient visit, emergency visit, and hospitalization
  - Date, reason, length of stay (for hospitalization)
- Prescribed medications
- Over-the-counter (OTC) medications
- Other therapies, e.g. oxygen therapy, nebulizers
- Associated costs if feasible
- Lab tests, image tests, surgeries, and other tests and procedures (e.g., spirometry, Chest X-Ray, CT)

Given the high co-morbidities among COPD patients, non-COPD healthcare resource utilization will also be captured by extracting data from the HIS/EMR complimented by tri-monthly patient interviews. Information collected include:

- Non-COPD outpatient visits and emergency visits
  - Number of visits, date of visit, diagnosis of visit
- Non-COPD hospitalization (including intensive care)
  - Number of hospitalization, date and length of stay, diagnosis of visit

### **9.2.11. Mortality**

[figure not shown]
Details of any patient deaths, including date of death, will be recorded in the CRF. Information will be obtained from the telephone interview and from medical records in HIS. Cause of death will be recorded if available. Data from publicly available source will be used if participant is not contactable at the end of the study.

## **9.3. Exacerbation Visits (sub-cohort only)**

Exacerbation visits only apply to subjects included in the Biomarker & Digital sub-cohort. Exacerbations that occur during the study will be detected through several pathways of reporting, including: direct contact with the study site or using a process of screening questions triggering a site alert and follow-up consultation, at which the investigator will determine whether the worsening of symptoms identified by evening diary meets the definition of a moderate/severe exacerbation and if it does then an exacerbation visit is scheduled. This triggering process is described in Section [9.2.6.2](#). Visit will be scheduled to occur within 72 hours of the alert (symptom onset) ([Figure 4](#)).

At the exacerbation Visit, the following study procedures will be completed: (1) PROs: e.g. the CAT, (2) blood sampling, (3) spirometry, (4) sputum sampling including induced sputum if required, (5) chest imaging, (6) healthcare resource utilization and cost including COPD medication and treatment. The sputum samples must be collected before the subjects receive antibiotics and/or systematic corticosteroids.

**Figure 4 Exacerbation Detection Through Evening Diary Questions**

After completion of study procedures at the AECOPD Visit, the investigator will administer treatment for the exacerbation. Follow-up phone call(s) will be made by the investigator to the participant at least every 2 weeks until the AECOPD has resolved. No more than 2 AECOPD experienced during the study will be evaluated. If a participant experiences another exacerbation while on study, then they are to contact their regular physician for treatment.

#### 9.4. Adverse Events

No study drug will be given in this study, only study procedure related serious adverse events (SAE) will be recorded. All SAEs will be collected from the signing of the ICF until the follow-up visit at the time points specified in the SoA ([Table 1](#)).

The investigator is responsible for the detection and documentation of events meeting the criteria and definition of an SAE, provided in this protocol. During the study when there is a safety evaluation, the investigator or site staff will be responsible for detecting, documenting and reporting SAEs.

Adverse Events (AE) will not be captured in the study. It is possible that participants could spontaneously describe potential adverse events that occurred during the course of study visits. As part of the site orientation process, study team members will be trained in the recognition of potentially-reportable adverse events. If an AE (serious or non-serious) or complaint with any specifically named GSK product is reported spontaneously by a subject during the course of the study, the site staff will complete the AE reporting form and transmit the report to the GSK China within 24 hours of being made aware of the AE.

AE is any untoward medical occurrence in a patient or clinical investigation subject, temporally associated with the use of a medicinal product, whether or not considered related to the medicinal product. An AE can therefore be any unfavourable and unintended sign (including an abnormal laboratory finding), symptom, or disease (new or exacerbated) temporally associated with the use of a medicinal product. For marketed

medicinal products, this also includes failure to produce expected benefits (i.e., lack of efficacy), abuse or misuse.

Serious Adverse Event (SAE) is defined as any untoward medical occurrence that, at any dose:

- Results in death,
- Is life-threatening,
- Requires hospitalization or prolongation of existing hospitalization,
- Results in disability/incapacity,
- Is a congenital anomaly/birth defect?
- Other: medical or scientific judgement should be exercised in deciding whether reporting is appropriate in other situations, such as important medical events that may not be immediately life-threatening or result in death or hospitalisation but may jeopardise the subject or may require medical or surgical intervention to prevent one of the other outcomes listed in the above definition. These should also be considered serious.
- Possible drug-induced liver injury

If an event is not an AE per definition above, then it cannot be an SAE even if serious conditions are met (e.g., hospitalization for signs/symptoms of the disease under study, death due to progression of disease, etc).

See study Pharmacovigilance Plan (sPVP) for details. sPVP will include the following elements to ensure a comprehensive approach to safety event collection and reporting:

Supplier pharmacovigilance training

Investigator and site staff pharmacovigilance training

Safety-specific roles

SAEs collection and reporting processes

SAEs collection forms

Frequency of data review

Reporting process and timelines

Interim reports

Study-specific PVP monitoring process

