8. Physical activity will be evaluated by daily steps as assessed by a wrist band dispensed at baseline. Participants are required to keep wearing the wrist band for 1 month from Visit 1 (baseline) and Visit 3
9. Daily digital EXACT measurement for 6 months from Visit 1 (baseline) and Visit 3
10. Monthly digital measurement from baseline for 6 months, and monthly digital measurement from V3 for 6 months
11. Sputum can be collected spontaneously or can be induced, as per investigator judgement. Sputum sampling should only be done if, in the opinion of the investigator, it is safe for the subject. No systemic corticosteroids or antibiotics used within 14 days before collecting the sputum sample. Participants who do not have a qualified sputum cytology sample at baseline will be requested to have a sputum cytology sample taken or re-sampled at V2 (Note: for COPD participants, they should be clinically stable and has no exacerbations for at least 30 days prior to sampling).
12. Only SAEs relating to the study procedures are collected.
13. No systemic corticosteroids or antibiotics used within 14 days before collecting the blood sample.

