## Risk Assessment

| Potential Risk of Clinical Significance  | Summary of Data/Rationale for Risk   | Mitigation Strategy   |
|--|--|---|
| Investigational Product (IP)  |  |   |
| No investigational product (IP) will be investigated in this study; thus, detailed information on IP is not applicable | Not applicable  | Not applicable   |
| Study Procedures  |  |   |
| Potential risk for injury with phlebotomy  | Risks with phlebotomy include bruising, bleeding, infection, and nerve damage.   | 
 
Procedures to be performed by trained personnel (i.e., study nurse)
 
   |
| Potential risk for sputum induction  | Risks associated with sputum induction include worsened expiratory airflow limitation and oxygen desaturation  | 
 
Sputum induction to be conducted in sub-cohort participants only.
 
Procedures to be performed by trained personnel (i.e., study nurse).
 
A standardized sputum induction protocol to be applied which have minimal deleterious effects on lung function and oxygen saturation and safety checks during the procedure.
 
 |
| Subjects exposed to ionising radiation as a consequence of participation in this study.                                | 
The ionising radiation exposure comes from repeated low dose CT scans of the chest.
 
Participants with COPD will be subject to a maximum of 6 scans, resulting in an effective dose of ionising radiation in the range 10-16mSv. This is equivalent
 | The study has been designed to keep the radiation dose as low as reasonably practicable (ALARP) whilst obtaining images of sufficient quality to meet the objectives. Participants <50 years of age will not be included in the sub-cohort, nor will females of child bearing potential. Healthy control participants will be   |

| Potential Risk of Clinical Significance | Summary of Data/Rationale for Risk  | Mitigation Strategy   |
|---|---|---|

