### Adverse Events

Adverse Events (AE) will not be captured in the study as no study drug will be given in this study.

- If an AE (serious or non-serious) or complaint with any specifically named GSK product is reported spontaneously by a subject during the course of the study, the site staff will complete the AE reporting form and transmit the report to the GSK China within 24 hours of being made aware of the AE.

Study procedure related serious adverse events (SAE) will be recorded.

- All SAEs will be collected from the signing of the ICF until the follow-up visit at the time points specified in the Schedule of Activities ([Appendix 2: Schedule of Activities](#))
- The investigator is responsible for the detection and documentation of events meeting the criteria and definition of an SAE, provided in this protocol. During the study when there is a safety evaluation, the investigator or site staff will be responsible for detecting, documenting, and reporting SAEs

Serious Adverse Event (SAE) is defined as any untoward medical occurrence that:

- Results in death,
- Is life-threatening,
- Requires hospitalization or prolongation of existing hospitalization,
- Results in disability/incapacity,
- Is a congenital anomaly/birth defect,
- Other: medical or scientific judgement should be exercised in deciding whether reporting is appropriate in other situations, such as important medical events that may not be immediately life-threatening or result in death or hospitalization but may jeopardize the subject or may require medical or surgical intervention to prevent one of the other outcomes listed in the above definition. These should also be considered serious.
- Possible drug-induced liver injury

See study Pharmacovigilance Plan (sPVP) for details. sPVP will include the following elements to ensure a comprehensive approach to safety event collection and reporting:

- Supplier pharmacovigilance training
- Investigator and site staff pharmacovigilance training
- Safety-specific roles

Adverse Events

• SAEs collection and reporting processes

• SAEs collection forms

• Frequency of data review

• Reporting process and timelines

• Interim reports

• Study-specific PVP monitoring process

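### Protocol Section 9.4 collects only procedure-related SAEs but defines an adverse event by timing relative to a medicinal product, so some procedure-related SAEs can be left out of the listing

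*Protocol*

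**What the plan says.** Protocol Section 9.4 opens with the recording rule: "No study drug will be given in this study, only study procedure related serious adverse events (SAE) will be recorded". Footnote 12 to the schedule of activities repeats it: "Only SAEs relating to the study procedures are collected".

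Section 9.4 then defines its terms. The adverse event definition is "AE is any untoward medical occurrence in a patient or clinical investigation subject, temporally associated with the use of a medicinal product". No causal link is required, and new or exacerbated disease counts, but study procedures are not mentioned. The SAE definition adds the usual seriousness criteria, with drug-trial dose wording. The section closes the definitions with: "If an event is not an AE per definition above, then it cannot be an SAE even if serious conditions are met". Its examples of such non-events are hospital admission for the underlying disease and death from its progression. Details are referred to a study pharmacovigilance plan.

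The SAP (Section 17.5.2, Adverse Events) states only "Serious Adverse Event (SAE) is defined as any untoward medical occurrence that" meets a seriousness criterion. It omits the medicinal-product definition, the dose wording and the closing sentence, but still tells the investigator to apply the definition in the protocol. SAP Section 15.1 plans a listing of procedure-related SAEs and a separate summary of deaths.

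**The concern.** The events to be collected are defined by study procedures, but the test for counting as an event is defined by drugs. In a drug trial the two usually coincide, because every participant takes a product. Here they need not: whether a serious injury from blood sampling, CT or the wrist band counts depends on whether the participant happened to use some medicine near that time.

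The disease example raises a second difficulty. The protocol's Risk Assessment table says: "Risks associated with sputum induction include worsened expiratory airflow limitation and oxygen desaturation". In a participant with COPD, those harms look like the disease itself. Two sites could classify the same post-induction admission differently, each with support from Section 9.4.

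What is at stake is whether the procedure-SAE listing is complete. Non-serious adverse events are not captured and Section 9.6 schedules no safety assessment, so a non-fatal serious procedure harm that fails the definition has no other planned safety table to appear in.

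**Working it through.** The plan has no figure to reproduce here. The check sets the provisions side by side and follows each type of event through them.

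**Provisions used.** (1) Recording rule: procedure-related SAEs only (Section 9.4; Table 1 footnote 12). (2) Adverse event test: temporal association with any medicinal product, regardless of causality, with no time window given (Section 9.4). (3) Gate: an event that is not an adverse event cannot be an SAE (Section 9.4). (4) Timing of procedures: Table 1, its footnotes, and Section 9.

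**Events followed through.**

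- *Serious event after blood sampling, sputum collection or HRCT on a day with spirometry.* Table 1 schedules these procedures only at visits that also have spirometry, and footnote 7 requires pre- and post-bronchodilator values at each site visit. A bronchodilator has been used, the timing test is met, and the gate does not operate. Recorded.
- *Serious event during wrist-band wear.* The band is worn for a month from Visit 1 and from Visit 3, mostly away from any clinic bronchodilator. The test is met only through the participant's own medication. The sub-cohort includes 50 healthy controls and a target of about 60 COPD participants without inhaled maintenance treatment. They may take other medicines, but the protocol does not ensure it. With no medicine nearby, the event is not an adverse event, so it is not an SAE, although the recording rule covers it. Can be dropped.
- *Serious event after a Visit 1 procedure on a different day from spirometry.* Visit 1 has a +7-day window, and Section 9 lets qualifying routine spirometry done before consent serve as baseline. Blood sampling or HRCT need not share a day with a bronchodilator. Can be dropped.
- *Admission for respiratory worsening after sputum induction in COPD.* By definition this is exacerbated disease, and on a bronchodilator day it passes the timing test. By the gate's own example, admission for the underlying disease lies outside. The two parts of Section 9.4 give different answers. Can be dropped, depending on how the site reads it.
- *Any of these under the SAP wording alone.* None is excluded. But the SAP defers to the protocol definition and can list only what sites recorded, so it does not restore dropped events.
- *Death.* Summarised separately in SAP Section 15.1, whatever the SAE definition says.

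**Where the gap can open, at planned numbers.** Wrist-band wear: 400 sub-cohort participants × 2 periods = 800 periods before dropout. Scheduled sputum collections in COPD: 100 + 100 + 50 = 250 participants, at Visits 1 and 4. That is 250 × 2 = 500 before dropout, or 250 + 250 × 0.75 = about 438 if the 25% dropout assumed in Section 10.1.3 has all occurred by Visit 4. An unstated share would be spontaneous rather than induced. These are counts of opportunities, not of expected events.

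**The case against.** The strongest reply is that a reader might infer that the definitions shut out procedure-related SAEs altogether, and the text does not say that. The link is to any medicinal product, is temporal, and needs no causal judgement. Every visit with blood sampling, sputum or HRCT also has a bronchodilator by design. The adverse event definition includes exacerbated disease, and the gate's examples appear aimed at the natural course of COPD. A reading that defeats the opening sentence of Section 9.4 is not the natural one, and sites are to be trained in recognising reportable events. The pharmacovigilance plan, which is not among the documents, may settle the matter.

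Most of this stands, and it narrows the point to the three routes shown above. It does not remove them. The bronchodilator does not reach a month of wrist-band wear or a Visit 1 spread over several days. The disease example remains in conflict with the definition it is meant to illustrate. Intent can be inferred from the opening sentence, but a protocol should not need another document to reverse its own definition.

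**Conclusion.** Section 9.4 is internally inconsistent. Its literal application can leave out some procedure-related SAEs that the same section and the schedule of activities say are collected. The effect is partial: it needs either no medicinal product used nearby or a site that classes a post-induction event as underlying disease. It also assumes that the pharmacovigilance plan does not already correct the definition.

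The number of events affected cannot be estimated. The documents give no rate for serious procedure harms, no split between induced and spontaneous sputum, and no basis for how often sites would apply the gate literally.

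Three stronger conclusions that a reader might draw are not supported:

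- The listing is not the only safety output, since deaths and their causes are summarised separately.
- It does not follow that sites or the sponsor would fail to act. Section 9 requires immediate safety concerns to be discussed with the sponsor at once, and Appendix 2 has ethics committees told of significant safety findings as well as SAEs, as their procedures require.
- The SAP does not set up a rival definition. It shortens the protocol's and refers back to it.

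The wording should be corrected because the remedy is small and the listing should be complete. The point does not bear on any endpoint, model or sample size.

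**What to change.** Reconcile protocol Section 9.4, footnote 12 to the schedule of activities and SAP Section 17.5.2:

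- For study SAEs, state that the definition covers any untoward occurrence temporally associated with a study procedure: blood sampling, spirometry with bronchodilator, sputum sampling or induction, HRCT, or the wrist band.
- State that the disease-under-study example does not apply where a study procedure may have contributed.
- Keep the medicinal-product wording for spontaneous reports on named sponsor products.
- Use the same definition in the SAP, and check that the pharmacovigilance plan agrees.

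The cost is a short wording change, brief site retraining and a few more SAE forms. If data are already in hand, comparing recorded hospitalisation dates (protocol Section 9.2.10) with procedure dates would show whether any candidate event was missed, as far as those dates were captured.
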